5.1.2 Day Numbering

Blinded Phase:

The first day of treatment (Day 1) will be taken from the Study Medication case report form (CRF) page at Visit 3. However, if this date is missing then the date of Visit 3 will be used.

Any days prior to Day 1 will be numbered relative to this day and calculated as:

Date - (Date of Day 1); to give Day -1, -2, -3 etc.

Any days post Day 1 will be calculated as:

1 + Date - (Date of Day 1)

Open-label Extension:

The first day of treatment in the OLE (OLE Day 1) will be day of entry into the OLE, which is expected to be the same day as the end of treatment visit from the blinded phase. OLE day will be calculated as above but relative to OLE Day 1.

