5.6.2 Adverse Events

All reported AEs will be classified by system organ class (SOC), preferred term and lower level term using Version 19.1 of MedDRA.

Summaries will be presented by treatment arm as well as SOC and preferred term.

A blinded phase treatment emergent AE (TEAE) is defined as an AE with a start date on or after the first dose of IMP during the blinded phase up to and including the date of first dose of the OLE phase (OLE Day 1). An OLE phase TEAE is defined as an AE with a start date on or after the OLE Day 1. If an AE has a partial start date and it is unclear from the partial date (or the stop date) whether the AE started prior to or post first dose of IMP then the AE will be considered treatment emergent and if it is unclear which phase the event started, it will be assigned to both phases. If the start date of the AE is the same as the date of first dose of IMP from the blinded phase and the plausible relationship to IMP is marked on the CRF as "Prior to study medication" then the AE will not be considered treatment emergent.

An AE will be considered treatment-related if the plausibility relationship to trial medication is recorded on the CRF as 'yes'. If the data on plausibility relationship to trial medication is missing then the AE will be considered treatment-related.

An AE will be considered leading to permanent discontinuation of IMP if the action taken with IMP is recorded on the CRF as 'study medication stopped' or the outcome is recorded on the CRF as 'patient died'.

An AE will be considered leading to IMP dose reduction excluding permanent discontinuation if the action taken with IMP is recorded on the CRF as 'dose reduced', 'dose reduced temporarily' or 'study medication interrupted'.

An AE will be considered leading to temporary IMP dose reduction if the action taken with IMP is recorded on the CRF as 'dose reduced temporarily'.

An AE will be considered leading to permanent IMP dose reduction excluding permanent discontinuation if the action taken with IMP is recorded on the CRF as 'dose reduced'.

An AE will be considered fatal if the outcome is recorded on the CRF as 'patient died'.

The following summaries will be generated separately for the blinded and OLE phase (counts are by patient unless specified otherwise):

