For eGFR, results will be assigned to the following grades:

- Normal: $>60 \text{ ml/min/1.73 m}^2$
- Grade 1: $60 \text{ ml/min/1.73 m}^2$
- Grade 2: ≥ 30 and $<60 \text{ ml/min/1.73 m}^2$
- Grade 3: ≥ 15 and $<30 \text{ ml/min/1.73 m}^2$
- Grade 4: $<15 \text{ ml/min/1.73 m}^2$

A separate shift table will be produced for eGFR based upon the above grades to determine the categorical shifts from baseline to each post-baseline visit.

For the blinded phase, scatter plots will be produced for each laboratory parameter presenting the maximum post baseline result divided by the upper limit of normal (ULN) on the Y-axis, and the baseline result divided by the ULN on the X-axis. However, for prothrombin international normalized ratio (INR), both axes will present the raw results rather than dividing by ULN.

An additional table will be produced for the blinded phase only, summarizing the number of patients meeting the following criteria:

- Alanine aminotransferase (ALT) $> 1 \times \text{ULN}$ at baseline
- Aspartate aminotransferase (AST) $> 1 \times \text{ULN}$ at baseline
- AT $> 1 \times \text{ULN}$ at baseline
- Treatment emergent ALT $> 3 \times \text{ULN}$, $> 5 \times \text{ULN}$ and $> 8 \times \text{ULN}$
- Treatment emergent AST $> 3 \times \text{ULN}$, $> 5 \times \text{ULN}$ and $> 8 \times \text{ULN}$
- Treatment emergent AT $> 3 \times \text{ULN}$, $> 5 \times \text{ULN}$ and $> 8 \times \text{ULN}$
- Treatment emergent AT $> 3 \times \text{ULN}$ and either bilirubin $> 2 \times \text{ULN}$ or INR > 1.5

where AT is AST or ALT, and treatment emergent is defined as criteria not met at baseline but met at any time post-baseline. The above will be summarized overall and for the following subgroups:

- Sex (Male, Female).

- Valproic acid use (Yes, No).
- Clobazam use (Yes, No).
- Valproic acid use and Clobazam use (Yes/Yes, Yes/No, No/Yes, No/No).
- Patients taking 3 or more current AEDs.
- Patients taking 4 or more current AEDs.

A separate table will be produced, by treatment arm and visit, presenting the incidence of patients with urinalysis or blood results indicative of a medical condition at Visit 1 and indicative of an adverse event after Visit 1.

All laboratory data will be listed; listings will include limited demographic information about the patient (age, sex, race and weight at baseline). Abnormal laboratory values will be listed separately.

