5.6.4.3 Physical Examination

Any relevant findings at screening are included as part of the patient's medical history. Any changes seen after screening that are indicative of an AE are to be recorded as such on the AE form and included as part of the AE summaries.

Additionally, height and weight are recorded as part of the physical examination. Height and weight will be summarized and listed together with the vital signs parameters.

Incidence of patients with a physical examination indicative of a medical condition at Visit 1 and indicative of an adverse event after Visit 1 will be summarized by treatment arm and visit.

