5.7.2 Pharmacokinetics of CBD and its Major Metabolites

Samples for PK analysis are taken on Visit 3 (first dose, Day 1) and Visit 10 (last maintenance dose of the blinded phase, Day 113) for patients weighing more than 20 kg. For patients recruited under Protocol Version 2, PK samples were taken at the following time-points:

- Prior to administration of IMP, ≤ 0.0 hours pre-dose on Visit 3 or C_{trough} at steady state (Visit 10).
- ≥ 4.0 hours to ≤ 5.0 hours.
- ≥ 6.0 hours to ≤ 7.0 hours.
- ≥ 8.0 hours to ≤ 10.0 hours, for patients 18 years or older.

Patients recruited under Protocol Version 3 onwards, PK samples were taken at the following time-points:

- Prior to administration of IMP, ≤ 0.0 hours pre-dose on Visit 3 or C_{trough} at steady state (Visit 10).
- ≥ 2.0 hours to ≤ 3.0 hours.
- ≥ 4.0 hours to ≤ 6.0 hours.
- ≥ 8.0 hours to ≤ 10.0 hours, for patients 18 years or older.

The nominal mid-point time of 0, 2.5, 4.5, 5, 6.5 and 9 hours will be used for summaries of plasma concentrations. Plasma concentrations and PK parameters will be summarized showing the number of non-missing values (n), arithmetic mean, standard deviation, coefficient of variation (%), median, minimum and maximum. Where samples are reported as BLQ, a value of zero will be used in the summaries. Summary statistics will be presented to 3 significant figures.

Where data allow, the PK parameter AUC_{0-t} , will be derived at each visit by the PK vendor. A dose-normalized AUC_{0-t} will be calculated as AUC_{0-t} divided by the randomized dose per administration (12.5 or 25 mg/kg). This will include Visit 3, for consistency, where the first dose of IMP will be 2.5 mg/kg.

Plasma concentrations of CBD and its major metabolites 7-hydroxy-CBD (7-OH-CBD) and 7-carboxy-CBD (7-COOH-CBD) will be summarized by nominal mid-point time, visit and GWP42003-P arm. In addition, a dot plot of plasma concentrations for each patient, by nominal mid-point time will be created for each visit and GWP42003-P arm. The arithmetic mean will be highlighted on the plot. Additionally, a line plot of the arithmetic mean plasma concentration will be created with standard error bars by nominal mid-point time for each visit and GWP42003-P arm. These plots will be presented both a linear and semi-logarithmic scale for plasma concentration.

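### Adverse events starting on OLE Day 1 are treatment-emergent in both phases, even when it is known whether they began before or after the first OLE dose

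*SAP*

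**What the plan says.** SAP Section 5.6.2 runs the blinded-phase TEAE window from the first blinded dose "up to and including the date of first dose of the OLE phase (OLE Day 1"). The next sentence sets the other window: "An OLE phase TEAE is defined as an AE with a start date on or after the OLE Day 1". Both bounds are calendar dates.

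Section 5.1.2 defines OLE Day 1 as the day of entry into the OLE, "which is expected to be the same day as the end of treatment visit from the blinded phase". Section 5.7.2 describes that visit as "Visit 10 (last maintenance dose of the blinded phase, Day 113").

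Section 5.6.2 has two rules for doubtful cases:

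- A same-day exemption, which opens "If the start date of the AE is the same as the date of first dose of IMP from the blinded phase". If the CRF also marks the event as preceding study medication, it is not treatment-emergent. No such rule is given for OLE Day 1.
- A rule for partial start dates: "if it is unclear which phase the event started, it will be assigned to both phases".

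Section 3.3.1 makes the incidence, type and severity of AEs the primary endpoint of the OLE. Section 5.1 reports OLE tables by earlier treatment (GWP42003-P or placebo) and overall.

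**The concern.** The two definitions should sort events by the treatment in force at onset. On the changeover day they do not. Blinded treatment is still in effect when the patient arrives at the end-of-treatment visit, and the first OLE dose is expected the same day. The SAP recognizes this kind of problem at the first blinded dose and solves it there with a CRF-based exemption, but leaves the second first-dose day without one.

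For patients from the active arms, the result is only a blurred phase boundary, since they were already on GWP42003-P. For placebo patients it changes the treatment to which the event is attributed, and it does so in both directions. An event from before any active drug enters the OLE primary endpoint. An event after the first active dose enters the placebo column of the randomized safety comparison.

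The visit is also one at which findings can become AEs. Section 5.6.4.3 says of physical examination: "Any changes seen after screening that are indicative of an AE are to be recorded as such on the AE form". Section 5.6.3.1 plans a by-visit table of laboratory results "indicative of a medical condition at Visit 1 and indicative of an adverse event after Visit 1", and the vital-sign and ECG sections plan similar tables.

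**Working it through.** The SAP gives no figure for this point, so the check is mainly one of logic.

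**1. Overlap of the windows.** Let D be OLE Day 1.

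- Blinded TEAE window: first blinded dose date to D, with D included.
- OLE TEAE window: D onward, with D included.
- Intersection: D alone, one calendar day. If entry falls on the planned end-of-treatment visit, D is Day 113, the last of the 113 treatment-period days in Section 5.1.3.4.

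**2. What happens to a placebo patient's event dated D.**

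| What is known about onset | Drug received by onset | Blinded TEAE? | OLE TEAE? | Result |
|---|---|---|---|---|
| Full date, known to precede first OLE dose | Placebo only | Yes | Yes | OLE count is wrong |
| Full date, known to follow first OLE dose | First GWP42003-P | Yes, as placebo | Yes | Blinded count is wrong |
| Full date, order unknown | Cannot be told | Yes | Yes | Defensible |
| Partial date, phase unclear | Cannot be told | Yes | Yes | Covered by the stated rule |

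The first two rows are the defect. The information to classify the event exists, and the definitions do not use it.

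**3. Whether another rule removes these cases.** The same-day exemption is tied to the first blinded dose, so it does not reach D. The assign-to-both rule concerns partial dates, so it is not the source of the overlap and does not explain it.

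**4. How many patients the placebo problem can reach.** Section 3.2 randomizes 210 patients 2:2:1:1. The two placebo arms together hold (1 + 1) / 6 × 210 = 70. This is a ceiling, because only those who enter the OLE can be affected.

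**5. What one patient is worth in the blinded comparison.** In an arm of 70, one patient is 1/70 = 1.4 percentage points. Section 5.6.2 plans a table of TEAEs seen in at least 2% (after rounding) of patients on GWP42003-P with incidence above placebo. As an illustration with 70 per arm, take a term reported by 2 patients on an active arm and 1 on placebo: 2/70 = 2.9% against 1/70 = 1.4%. It meets both conditions. One post-dose OLE Day 1 event in a different placebo patient makes placebo 2/70 = 2.9%, and that arm no longer exceeds placebo. This shows how sensitive an uncommon term is. It does not predict that such a case will occur.

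**The case against.** The best defense is that the inclusive bounds were chosen on purpose. The wording of the blinded window is explicit, and it fits a plan that sends events of unclear phase to both phases and takes the worst case for missing severity or causality. Where only the date is known, counting the event in both phases is reasonable safety reporting, and that part stands. It does not justify counting in both phases an event whose order is known. Nor is it conservative in the second direction, where an event after first active drug raises the placebo rate. The SAP gives no rationale for fully dated events.

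Several limits on the consequence also stand:

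- A reader might infer that OLE incidence is inflated by double counting. The summaries are produced separately by phase, and no listed AE table pools the phases, so no event is counted twice in one table. Counts are by patient unless stated otherwise. A patient's overall OLE incidence changes only if the Day 1 event is that patient's sole OLE TEAE, and a preferred-term count changes only if the term does not recur for that patient in the OLE. The by-event tables do gain the event.
- The OLE AE analysis is descriptive, and no OLE hypothesis stands in the testing hierarchy.
- Listings show AE start day, so events dated OLE Day 1 can be found afterwards.
- A reader might infer that AE dates cluster at the end-of-treatment visit. The SAP makes this possible but does not establish it: neither the abnormality tables nor the physical examination text says that a finding takes the visit date as its onset.

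**Conclusion.** The point holds as a classification error confined to one day. A fully dated AE on OLE Day 1 is a TEAE in both phases even when it is known on which side of the first OLE dose it began, and for placebo patients this assigns it to the wrong treatment in one of the two sets of tables.

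Its size cannot be derived from the SAP. It is bounded by a single calendar day, by one appearance per phase, and by about 70 patients for the placebo problem. It rests on two conditions: that OLE Day 1 coincides with the end-of-treatment visit, which the SAP expects but does not guarantee for every patient, and that the recorded start date is that day. A finding dated earlier falls in the blinded phase only.

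Two stronger readings are not supported. One could assume that, say, 3–10% of 210 patients (6–21) have such an event. The SAP gives no rate, the base is everyone randomized and not those entering the OLE, and the share would mix onsets before and after the dose. One could also infer that these events land in the earliest OLE onset category. Section 5.6.2 counts onset from the first dose of IMP without saying that this means the first OLE dose in the OLE tables. Read literally, an event on Day 113 falls in the category beyond 12 weeks.

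The correction is still worth making, because AE incidence is the OLE primary endpoint and the remedy costs very little.

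**What to change.** In Section 5.6.2, add a rule for AEs with a complete start date of OLE Day 1. Use the recorded onset time, or a pre-dose flag modeled on the existing exemption for the first blinded dose:

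- known to precede the first OLE dose: blinded phase only;
- known to follow it: OLE only;
- order unknown, because the onset is untimed or the date is partial: both phases, as now.

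Report how many events are shared between the phases.

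Untimed OLE Day 1 events should not be sent to the blinded phase by default. That would attribute a possible reaction to a placebo patient's first active dose to placebo alone and remove it from OLE safety.

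The cost is a short addition to the text, a change to the phase flag, and a small amount of extra flagging. Section 5.1.1.3 speaks of AE dates and times, so onset times may be available, but the SAP does not confirm this. If they are not, the pre-dose flag serves instead. The remaining weakness is that untimed events of that day stay in both phases, with their number visible.

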3. INVESTIGATIONAL PLAN

3.1 Trial Design

This multicenter trial consists of a randomized, placebo-controlled, double-blind phase followed by an open-label extension (OLE) phase.

Blinded Phase:

The blinded phase of the trial is a randomized, double-blind, parallel-group, 16-week comparison of two doses of GWP42003-P vs. placebo. Patients will complete a 1-week screening period and a 4-week baseline period before they are randomized to receive either 25 mg/kg/day GWP42003-P, 50 mg/kg/day GWP42003 P or placebo. Randomization will be stratified by age according to the following ranges: 1–6, 7–11, 12–17 years and 18–65 years. Patients will begin a 4-week dose escalation period, titrating up to their assigned dose, before continuing on a stable dose of blinded Investigational Medicinal Product (IMP) for 12 weeks.

Dose escalation for each patient is subject to the investigator's assessment of safety and tolerability. If a dose becomes poorly tolerated, the investigator may consider temporarily or permanently reducing the dose for the remainder of the trial.

Following completion of the blinded phase, patients will be invited to continue to receive GWP42003-P in an OLE.

Those patients opting not to enter the OLE will complete a 10-day taper period (down-titrating 10% per day for 10 days).

Open-label Extension Transition:

In order to maintain consistent exposure to IMP and maintain the integrity of the blind, patients will enter a 2-week blinded transition to the OLE. OLE IMP will be titrated up to 25 mg/kg/day whilst blinded IMP is simultaneously tapered down to zero. All patients will complete the transition and enter the OLE taking 25 mg/kg/day GWP42003-P:

- Patients from the placebo arm will titrate up to 25 mg/kg/day GWP42003-P.
- Patients from the 25 mg/kg/day GWP42003-P arm will continue to take 25 mg/kg/day GWP42003-P.
- Patients from the 50 mg/kg/day GWP42003-P arm will taper down (10% per day) to 25 mg/kg/day GWP42003-P.

Open-label Extension:

The OLE consists of a 3-week titration period followed by a maintenance period and a 10-day taper period. The initial OLE period will last for a maximum of 1 year.

Following titration according to the titration schedule, patients will continue with their optimal GWP42003-P dose. However, investigators may decrease the dose if a patient experiences intolerance, or increase the dose to a maximum of 50 mg/kg/day if required for better seizure control, until the optimal dose is found.

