5. STATISTICAL METHODS

5.1 General Considerations

In all tables, listings and figures for the double-blind phase, the trial medications will be referred to and labelled as per Table 1.

Table 1 Blinded Phase Trial Treatments

Endpoint	Actual Treatment	Treatment Label
Efficacy	Pooled Placebo	Placebo
Safety	25 mg/kg/day Placebo	Placebo 25 mg/kg
	50 mg/kg/day Placebo	Placebo 50 mg/kg
All	25 mg/kg/day GWP42003-P	25 mg/kg
All	50 mg/kg/day GWP42003-P	50 mg/kg

For safety tables where placebo is split by dosing volume, an additional Pooled Placebo column will be included.

For OLE tables, columns will be included for treatment received during the double-blind phase (GWP42003-P or placebo, i.e. not split by dose) and overall.

In all tables, listings and figures, the trial visits will be referred to and labelled as per Table 2.

Table 2 Trial Visits

Actual Visit	Visit Label
Visit 1: Screening	Day -35
Visit 2: Day -28, baseline visit	Day -28
Visit 3: Day 1, Randomization	Day 1
Visit 4: Day 15	Day 15
Visit 5: Day 29	Day 29
Visit 6: Day 43	Day 43
Visit 7: Day 57	Day 57
Visit 8: Day 71, Telephone	Day 71
Visit 9: Day 85	Day 85
Visit 10: Day 113	End of Treatment
Visit 11: Day 123	End of Taper
Visit 12: Day 151	Safety Follow-Up
Visit B1: Day 1, Enrollment	OLE Day 1
Visit B2: Day 15	OLE Day 15
Visit B3: Day 36	OLE Day 36
Visit B4: Day 92	OLE Day 92
Visit B5: Day 141, Re-stocking of supplies	OLE Day 141
Visit B6: Day 183	OLE Day 183
Visit B7: Day 232, Re-stocking of supplies	OLE Day 232
Visit B8: Day 274	OLE Day 274
Visit B9: Day 323, Re-stocking of supplies	OLE Day 323
Visit B10: Day 365	OLE End of Treatment
Visit B11: Day 375	OLE End of Taper
Visit B12: Day 389	OLE Post-taper Safety Telephone Call
Day 403	OLE Follow-Up

Unless stated otherwise, continuous variables will be summarized showing the number of non-missing values (n), mean, standard deviation, median, minimum and maximum and categorical variables will be summarized showing the number and percentage of patients falling in each category. For continuous summaries of seizure frequency, the lower and upper quartiles will also be presented.

Minimum and maximum values will be presented to the same decimal precision as the raw data. Mean and median will be presented to one more decimal place than the raw data, and standard deviation to 2 more decimal places than the raw data. Percentages will be presented to one decimal place.

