The assumptions of normality and homogeneity of variance, for endpoints analyzed using parametric tests, will be checked where appropriate via examination of residual plots as well as computation of summary statistics for normality using the Shapiro-Wilk statistical test. If assumptions are violated then alternative non-parametric techniques will be used. In this instance the original parametric tests will be presented as a sensitivity analysis.

Open-label Extension:

All endpoints will be summarized on the OLE safety analysis set, unless specified otherwise.

Endpoints will be summarized by treatment received during the double-blind phase (GWP42003-P or Placebo, i.e. not split by dose) and overall.

For seizure endpoints, the OLE treatment phase will be split into 12 week periods, for example:

- OLE Week 1 (OLE Day 1) to OLE Week 12 (Day 84)
- OLE Week 13 (OLE Day 85) to OLE Week 24 (OLE Day 168)
- OLE Week 25 (OLE Day 169) to OLE Week 36 (OLE Day 252)
- OLE Week 37 (OLE Day 253) to OLE Week 48 (OLE Day 336)
- OLE Week 49 (OLE Day 337) to OLE Week 60 (OLE Day 420)
- Etc.

In addition, seizure data will be presented for the full OLE treatment phase as well as the last 12 weeks of the OLE treatment phase (see Section 5.1.3.3).

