- Overall summary of AEs, including number of patients reporting each of; TEAEs, treatment related TEAEs, TEAEs leading to withdrawal, treatment related TEAEs leading to withdrawal, serious TEAEs, treatment related serious TEAEs.
- Summary of TEAEs.
- Summary of TEAEs by event.
- Summary of treatment-related TEAEs.
- Summary of treatment-related TEAEs by event.
- Summary of TEAEs by maximal severity.
- Summary of TEAEs by sex.
- Summary of serious TEAEs.
- Summary of serious TEAEs by event.
- Summary of non-serious TEAEs.
- Summary of non-serious TEAEs by event.
- Summary of treatment-related serious TEAEs.
- Summary of treatment-related serious TEAEs by event.
- Summary of TEAEs leading to permanent discontinuation of IMP.

- Summary of treatment-related TEAEs leading to permanent discontinuation of IMP.
- Summary of TEAEs leading to IMP dose reduction excluding permanent discontinuation (by resolution and overall).
- Summary of treatment-related TEAEs leading to IMP dose reduction excluding permanent discontinuation (by resolution and overall).
- Summary of TEAEs leading to temporary IMP dose reduction (by resolution and overall).
- Summary of treatment-related TEAEs leading to temporary IMP dose reduction (by resolution and overall).
- Summary of TEAEs leading to permanent IMP dose reduction excluding permanent discontinuation (by resolution and overall).
- Summary of treatment-related TEAEs leading to permanent IMP dose reduction excluding permanent discontinuation (by resolution and overall).
- Summary of fatal TEAEs.
- Summary of TEAEs by time of first onset of AE.
- Summary of TEAEs by time to AE resolution.
- Summary of TEAEs reported in $\geq 2\%$ of patients (after rounding) in the GWP42003-P treatment arms and where the incidence is greater than the placebo treatment arm.
- List of patients experiencing TEAEs by SOC and preferred term.
- Summary of pre-treatment AEs (blinded phase only).

For the summary of TEAEs by maximal severity, for each patient, the worst severity recorded by preferred term, SOC and overall will be used for summary purposes. If severity is missing, the worst case (severe) will be assumed.

For summaries by resolution, AEs with an outcome of 'recovered' or 'recovered with sequelae' will be summarized as 'Resolved' and AEs with an outcome of 'continuing', 'patient died' or those with a missing outcome will be summarized as 'Not resolved'.

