OLE Table 11.2	Summary of Treatment Emergent Adverse Events	OLE Safety Analysis Set
OLE Table 11.3	Summary of Treatment-Related Treatment Emergent Adverse Events	OLE Safety Analysis Set
OLE Table 11.4	Summary of Treatment Emergent Adverse Events by Maximal Severity	OLE Safety Analysis Set

Table Number	Title	Analysis Set
OLE Table 11.5	Summary of Treatment Emergent Adverse Events by Sex	OLE Safety Analysis Set
OLE Table 11.6	Summary of TEAEs by Time of First Onset of AE	OLE Safety Analysis Set
OLE Table 11.7	Summary of TEAEs by Time to AE Resolution	OLE Safety Analysis Set
OLE Table 11.8	Summary of TEAEs Reported in $\geq 2\%$ of Patients in the GWP42003-P Treatment Arms	OLE Safety Analysis Set
OLE Table 11.9	Summary of Non-Serious Treatment Emergent Adverse Events	OLE Safety Analysis Set
OLE Table 11.10	List of Patients Experiencing Treatment Emergent Adverse Events by System Organ Class and Preferred term	OLE Safety Analysis Set
OLE Table 11.11	Summary of Treatment Emergent Adverse Events by Event	OLE Safety Analysis Set
OLE Table 11.12	Summary of Treatment-Related Treatment Emergent Adverse Events by Event	OLE Safety Analysis Set
OLE Table 11.13	Summary of Non-Serious Treatment Emergent Adverse Events by Event	OLE Safety Analysis Set
OLE Table 12.1	Summary of Serious Treatment Emergent Adverse Events	OLE Safety Analysis Set
OLE Table 12.2	Summary of Treatment-Related Serious Treatment Emergent Adverse Events	OLE Safety Analysis Set
OLE Table 12.3	Summary of Treatment Emergent Adverse Events Leading to Permanent Discontinuation of IMP	OLE Safety Analysis Set
OLE Table 12.4	Summary of Treatment-Related Treatment Emergent Adverse Events Leading to Permanent Discontinuation of IMP	OLE Safety Analysis Set
OLE Table 12.5	Summary of Treatment Emergent Adverse Events Leading to IMP Dose Reduction Excluding Permanent Discontinuation and by Resolution and Overall	OLE Safety Analysis Set
OLE Table 12.6	Summary of Treatment-Related Treatment Emergent Adverse Events Leading to IMP Dose Reduction Excluding Permanent Discontinuation and by Resolution and Overall	OLE Safety Analysis Set
OLE Table 12.7	Summary of Treatment Emergent Adverse Events Leading to Temporary IMP Dose Reduction by Resolution and Overall	OLE Safety Analysis Set
OLE Table 12.8	Summary of Treatment-Related Treatment Emergent Adverse Events Leading to Temporary IMP Dose Reduction by Resolution and Overall	OLE Safety Analysis Set

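### OLE Table 11.8 inherits a greater-than-placebo filter, although the OLE has no placebo arm and its placebo column holds new starters on GWP42003-P

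*SAP*

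**What the plan says.** SAP Section 5.6.2 introduces its list of adverse event tables with "The following summaries will be generated separately for the blinded and OLE phase". One item is the summary of TEAEs reported in at least 2% of patients (after rounding) "in the GWP42003-P treatment arms and where the incidence is greater than the placebo treatment arm". The only item in the list marked as belonging to the blinded phase alone is the pre-treatment AE summary; the common-TEAE item has no such mark.

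Appendix 6 (Table 18) then lists "OLE Table 11.8" on the OLE safety analysis set, with the same short title as Table 11.8 of the blinded phase. The SAP gives no separate selection rule for the OLE version.

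For OLE tables, Section 5.1 says "columns will be included for treatment received during the double-blind phase (GWP42003-P or placebo, i.e. not split by dose) and overall", and Section 5.5.1 repeats this grouping. On what the former-placebo patients take, Section 3.1 says: "Patients from the placebo arm will titrate up to 25 mg/kg/day GWP42003-P".

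**The concern.** In the blinded phase the filter makes sense. Placebo is a concurrent randomized control, and dropping events no more frequent on drug than on placebo removes background noise. In the OLE the same words have no valid comparator. Every patient takes GWP42003-P, so the comparison is between people continuing the drug and people starting it.

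If starting the drug brings its own adverse events, they will tend to be more frequent among new starters, and the filter removes exactly that pattern. Events that stay in the table do so because of a contrast between two active-drug groups, which says nothing about whether the drug caused them. A reader who uses the table for a short view of common OLE events could get an incomplete one. The incidence, type and severity of AEs is the OLE primary endpoint (Section 3.3.1), and Section 5.1.4 allows interim OLE reporting from a subset of outputs under the same SAP rules.

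**Working it through.** The SAP gives no figure to reproduce here. The check is a reading of the cross-references, followed by an illustration of how the rule behaves.

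**Does the rule reach the OLE?** Section 5.6.2 generates its list for both phases, restricts only the pre-treatment item, and Appendix 6 schedules the OLE table. The title of OLE Table 11.8 states only the 2% condition, but the blinded Table 11.8 has the same short title, so the title does not lift the placebo condition.

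**What is the placebo group in the OLE?** It is the column of patients who received placebo in the double-blind phase (Sections 5.1 and 5.5.1). Another sentence in Section 5.1 describes OLE tables by randomized arm rather than with the doses pooled. Under either grouping the placebo column is former-placebo patients.

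**Is their first exposure counted?** Yes. Section 5.1.2 sets OLE Day 1 at entry to the OLE, expected on the day of the blinded end-of-treatment visit. Section 5.6.2 counts OLE TEAEs from that day.

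**Single-event illustration.** Assumptions not in the SAP: all patients enter the OLE (from the planned 70 per arm in Section 3.2, 140 prior GWP42003-P and 70 prior placebo), and the incidences are chosen for the example.

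- Continuing patients: 21/140 = 15%
- New starters: 21/70 = 30%
- Overall: (21 + 21)/210 = 42/210 = 20%, and 20%/2% = 10 times the threshold
- Result: omitted, because 15% is not greater than 30%

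**Chance of omission.** Let X be the number of continuing patients with the event, binomial (n_A, p_A), and Y the number of new starters with it, binomial (n_P, p_P), independent. The event is kept if X/n_A, rounded to a whole percent, is at least 2% and X/n_A > Y/n_P. Then

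P(omitted) = 1 − Σ P(X = x) P(Y = y), summed over the pairs (x, y) that are kept.

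| Assumed true incidence: continuing / new starters | 140 / 70 enter | 112 / 63 enter | 100 / 50 enter |
|---|---|---|---|
| 10% / 10% | 0.524 | 0.490 | 0.528 |
| 20% / 20% | 0.519 | 0.498 | 0.523 |
| 5% / 10% | 0.913 | 0.884 | 0.880 |
| 10% / 15% | 0.861 | 0.829 | 0.825 |
| 10% / 20% | 0.975 | 0.963 | 0.953 |
| 15% / 30% | 0.994 | 0.989 | 0.984 |
| 25% / 30% | 0.791 | 0.762 | 0.758 |

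The smaller group sizes are also assumed. They are shown because not everyone need enter the OLE, and Section 2.3.3 of the SAP addendum reports more withdrawals in each active arm than on placebo.

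An event truly equally common in both columns is kept or lost at about even odds. One more common in new starters is omitted in roughly 76% to 99% of cases across these scenarios. For contrast, in the blinded phase with 140 on drug and 70 on true placebo, an event at 20% against 10% would be omitted with probability 0.027.

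**The case against.** The best reply is that nothing is lost from the report. OLE Tables 11.1, 11.2, 11.3, 11.4, 11.10 and 11.11 and OLE Listing 11.1.1 cover TEAEs overall, by relatedness, by maximal severity, by patient and by event, and none has a placebo condition. An event at 15% against 30% would appear in full in OLE Table 11.2. This stands. A reader might infer that genuine drug reactions vanish from the OLE safety results, or that the OLE primary endpoint is compromised; the documents do not support either. Nor do they give Table 11.8 any special status: it is one item in a long list, with no inference or decision attached.

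A second reply is that the placebo clause cannot apply where there is no placebo arm, so a programmer would apply 2% to all OLE patients. That is possible, but the SAP does not say so, and the OLE tables do have a column labelled by prior placebo treatment to which the clause can be applied. If the clause is instead ignored, the OLE rule has to be invented during programming. One clarifying sentence is needed either way.

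A third reply concerns direction. The initial OLE lasts up to 1 year and its TEAEs accumulate from OLE Day 1, so first-exposure events are pooled with months of later ones in both columns. The SAP has no incidence data showing that new starters will have more events. This also stands: a higher incidence in new starters is plausible but assumed.

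**Conclusion.** Wrong as written, of minor severity. Section 5.6.2 carries a placebo-controlled selection rule into a phase with no placebo control. Applied literally, OLE Table 11.8 omits every TEAE whose incidence in new starters equals or exceeds that in continuing patients, whatever its overall frequency. The table can therefore under-represent events at first exposure.

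That the rule lacks a valid comparator follows from the SAP's text and needs no assumption. How many events would be affected cannot be known from the documents: the 15% and 30% incidences, the group sizes and the omission probabilities are illustrations of the rule, not estimates of harm. The effect is confined to one descriptive table. No hypothesis test, effect estimate or analysis set changes, and the complete OLE adverse event output is intact.

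**What to change.** In Section 5.6.2, state that the greater-than-placebo condition applies to the blinded-phase table only. Define OLE Table 11.8 as all TEAEs with incidence of at least 2% in the overall OLE column, or alternatively in either prior-treatment column, and choose one of these in the text. Show both prior-treatment columns and the overall column. Retitle the table in Appendix 6 so that it no longer refers to GWP42003-P treatment arms, since every OLE patient takes GWP42003-P.

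The cost is one sentence and one table title, with no new data and no effect on any efficacy result or on type I error. The only downside is a somewhat longer table.
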